11.4 Notification of Adverse Events

Sponsor Notification:

The investigational center staff must report all AEs to Medtronic in a timely manner. All severe hypoglycemia, DKA, SAE, SADE, and DD with SADE potential should be reported immediately to Medtronic (but not later than 72 hours). For the previously mentioned events, the AE eCRF will be completed with all known details as soon as possible, this will serve as notification to Medtronic. If the study database cannot be accessed due to technical problems, contact the sponsor via email at [contact] and provide the de-identified known details of the event. Once the access issue has been corrected, the event should be entered onto an AE eCRF.

Source documents that support the event (e.g., clinic notes, hospital admission and discharge records, lab reports, EMT reports, ER/Urgent Care) should be provided to the sponsor via Medtronic's secure upload application. All source documents/medical records should be redacted of patient identifiers (full name, address, etc.) prior to providing to the sponsor. Each source page should be identified with the subject ID.

CIP342 Clinical Investigation Plan			
D00674412	Version E	Page 67 of 96	Medtronic

Table 8. Investigator Reports to Sponsor

Event 1	Type To Report	Timeframe for Reporting
•	Serious Adverse Device Effect (SADE)	
•	Unanticipated Serious Adverse Device Effect (USADE)	Immediately, but no later than 72 hours after
•	Serious Adverse Event (SAE)	investigational site study personnel's awareness
•	Adverse Device Effect (ADE)	of the event (or sooner if required by local
•	Device Deficiency that might have led to a SADE (see	regulation)
	Section 13)	
•	Adverse Event (AE)	In a timely manner from the investigator's /
•	Device Deficiency (DD) (see Section 13)	site's first knowledge of the event

Sponsor Reports:

Regulatory reporting of AEs and DDs will according to local regulatory requirements.

In countries following EU MDR 2017/745, AEs will be reported according to EU MDR 2017/745 Art. 80(2) and Medical Device Coordination Group (MDCG) 2020-10/1 guidance and additional local requirements if applicable.

In accordance with EU MDR Art. 80(2) the following events are considered reportable:

- a) any serious adverse event that has a causal relationship with the investigational device, the comparator or the investigation procedure or where such causal relationship is reasonably possible;
- b) any device deficiency that might have led to a serious adverse event if appropriate action had not been taken, intervention had not occurred, or circumstances had been less fortunate;
- c) any new findings in relation to any event referred to in points a) and b).

Table 9. Sponsor Adverse Events Reporting Requirements to National Competent Authority

Events To Report in EU/EEA	Reporting Requirements and Timeframe
 Any device and/or procedure related Serious Adverse Events (SAE) and/or Device Deficiency (DD) that may have led to a SADE which indicates an imminent risk of death, serious injury, or serious illness and that requires prompt remedial action for other patients/subjects, users or other persons or a new finding to it (occurred in the study under same CIP) 	Immediately, but no later than 2 calendar days after awareness by sponsor of a new reportable event or of new information in relation with an already reported event
 Any device and/or procedure related SAE and DD that may have led to an SADE (occurred in the study under same CIP*) – including updates 	Immediately, but not later than 7 calendar days after awareness
Events To Report in UK	Reporting Requirements and Timeframe

D00674412	Version E	Page 68 of 96		Medtronic
 Any SAE and/or DD that may hav which indicates an imminent risk injury, or serious illness and that remedial action for other patients or other persons or a new finding in the study under same CIP) 	e led to a SADE of death, serious requires prompt /subjects, users g to it (occurred	Immediately, but no later than awareness by sponsor of a new of new information in relation reported event	2 calenda reportal with an	ar days after ble event or already
 Any SAE and DD that may have (occurred in the study under sar including updates 	ed to an SADE ne CIP*)–	Immediately, but not later tha after awareness by the sponse reportable event or of new info with an already reported event	n 7 cale or of the ormation t	ndar days new in relation
 All SAEs 		Quarterly report according to C objection'. Quarterly after CA a	CA `letter approval	of no date

In addition, it is the responsibility of the investigator and the sponsor to abide by the AE reporting requirements stipulated by local law and the study site's EC.

11.5 Adverse Event and Device Deficiency Classification

All AEs and DDs will be reviewed by sponsor and will be classified according to the responsibilities as outlined below in **Table 10**.

Upon sponsor's receipt of an event, a Safety representative will review the AE/DD for completeness and accuracy and when necessary, will request clarification and/or additional information from the Investigator.

It is the responsibility of the investigator and sponsor to abide by any additional AE reporting requirements stipulated by the EC and RA responsible for oversight of the study.

What is classified?	Who classifies?	Classification Parameters		
Relatedness	Investigator	Device, Procedure, Outside Standard of Care CIP procedure		
	Sponsor	Device, Procedure, Outside Standard of Care CIP procedure		
Seriousness	Investigator	SAE, DD with SADE potential		
	Sponsor	SAE, USADE, and DD with SADE potential		
Diagnosis	Investigator	Based on presenting signs and symptoms and other supporting		
		data		
	Sponsor	MedDRA term assigned based on the data provided by Investigator		

Table 10. Adverse Event Classification Responsibilities

11.6 Causality Assessment

An AE is not automatically related to the study device or procedure simply because the subject is wearing the device and participating in the study. The event should be reviewed to determine if the device or study procedure could have possibly caused the event and therefore is related to the study device or procedure.

D00674412	Version E	Page 69 of 96	Medtronic
D00074412		1 age 03 01 30	

Causality assessment is the determination of the relationship between an AE and the device being studied. It is expected that the investigational center will review all elements surrounding the AE to properly assess the causality of the event to the study device or to a study procedure. The eCRF may be used as original source data for the assessment of causality and severity.

This review would include the subjects' (or parent/legal guardian) description of the event, study device uploads and medical records (if applicable) from the treating facility. These records will be made available to sponsor.

Investigators should classify the relationship between the AE and the study device or study procedures using one of the four possible causality categories listed below:

- **Not related:** relationship to the device, comparator, or procedures can be excluded when:
 - the event has no temporal relationship with the use of the investigational device or the procedures related to the application of the investigational device;
 - the event does not follow a known response pattern to the medical device (if the response pattern is previously known) and is biologically implausible;
 - the discontinuation of medical device application or the reduction of the level of activation/exposure – when clinically feasible – and reintroduction of its use (or increase of the level of activation/exposure), do not impact on the event;
 - the event involves a body-site or an organ not expected to be affected by the device or procedure;
 - the event can be attributed to another cause (e.g., an underlying or concurrent illness/ clinical condition, an effect of another device, drug, treatment or other risk factors);
 - the event does not depend on a false result given by the investigational device used for diagnosis, when applicable;

In order to establish the non-relatedness, not all the criteria listed above might be met at the same time, depending on the type of device/procedures and the event.

- **Possible:** the relationship with the use of the investigational device, comparator, or the relationship with procedures, is weak but cannot be ruled out completely. Alternative causes are also possible (e.g., an underlying or concurrent illness/clinical condition or/and an effect of another device, drug or treatment). Cases where relatedness cannot be assessed, or no information has been obtained should also be classified as possible.
- **Probable**: the relationship with the use of the investigational device, comparator, or the relationship with procedures, seems relevant and/or the event cannot reasonably be explained by another cause.

- **Causal relationship:** the event is associated with the investigational device, comparator, or with procedures beyond reasonable doubt when:
 - the event is a known side effect of the product category the device belongs to or of similar devices and procedures;
 - the event has a temporal relationship with investigational device use/application or procedures;
 - the event involves a body-site or organ that
 - the investigational device or procedures are applied to;
 - the investigational device or procedures have an effect on;
 - the event follows a known response pattern to the medical device (if the response pattern is previously known);
 - the discontinuation of medical device application (or reduction of the level of activation/exposure) and reintroduction of its use (or increase of the level of activation/exposure), impact on the event (when clinically feasible);
 - other possible causes (e.g., an underlying or concurrent illness/clinical condition or/and an effect of another device, drug or treatment) have been adequately ruled out;
 - harm to the subject is due to error in use;
 - the event depends on a false result given by the investigational device used for diagnosis, when applicable;

In order to establish the relatedness, not all the criteria listed above might be met at the same time, depending on the type of device/procedures and the event.

11.7 Anticipated or Unanticipated

If an AE is determined to be related to the study device the sponsor will then assess the event to determine if it is anticipated or unanticipated.

- **Anticipated:** the event is identified in the CIP; labeling; Investigator's Brochure (IB) or user guide.
- **Unanticipated:** the event has not been previously identified in the CIP; labeling; IB or user guide.

12 Data Review Committees

12.1 Clinical Events Committee

A CEC consisting of external physicians with an expertise in endocrinology and the management of diabetes including insulin pumps and CGM will be convened. The CEC will review AEs as required per protocol, which include reports of:

- Serious adverse event
- Serious adverse device effect
- Unanticipated serious adverse device effect (USADE)
- Severe hypoglycemia

D00674412

Version E

• Diabetic ketoacidosis

The CEC will assess events to determine agreement or disagreement with the investigator classification of an event.

If the CEC disagrees with the investigator's classification of the event, the rationale will be provided to the investigator. If the investigator agrees with the CEC's adjudication, the CRF documenting the AE will be updated accordingly.

If the investigator does not agree with the CEC's adjudication classification, both determinations will be provided within the final report; however, the CEC's adjudication will be used for data analysis. The disagreement will also be included in reporting to Ecs and regulatory authorities, if required.

The CEC may review applicable information for device related AEs which may include:

- Whether or not the event was unanticipated
- Review of sensor data from CareLink Personal/CareLink system software report (when applicable)
- Review of pump data from CareLink Personal/CareLink system software report (when applicable)
- Misuse of the device by the user

Review of events may require the following information. Final disposition may be delayed based on obtaining this information:

- Monitoring by sponsor at investigational center
- Device return and failure analysis
- CareLink Personal/CareLink system software upload and review of software reports
- Subject clarification to investigational center regarding details about the event
- Source documents that support event: Paramedic records; ER records; Lab records; Hospital

admission and discharge summary

12.2 Data Monitoring Committee

A Data Monitoring Committee (DMC) consisting of external physicians with an expertise in Endocrinology and the management of insulin-requiring diabetes including pump and CGM therapy, will be convened to review study progress and safety. The board will convene periodically. The DMC Charter is available under a separate cover.

The DMC will perform 2 main functions:

First: DMC will track and trend the overall safety of the study.

Event rate, defined as number of events per 100 patient years will be reviewed by the DMC with respect to the following:

• Event rate of all SAE
D00674412

- Event rate of severe hypoglycemia
- Event rate of DKA
- Event rate of device related AE

Second: Based on their meeting, DMC will recommend a decision to the sponsor regarding the following:

- Whether or not enrollment should be halted.
- Whether or not the entire study will need to be stopped including for those subjects who have received study devices already.

12.3 Central Lab

This information may be subject to change during the course of the study. Periodic updates to study contact information will be sent to study sites as needed.

Table 11. Core Laboratory Information

Contact Information	Role
ACM Global Laboratories	Analysis of HbA1c samples collected during the
	Continuation Phase

13 Device Deficiencies

The subject's parent/legal guardian will be instructed to contact the investigational center staff for questions or concerns regarding study devices.

All device deficiencies will be collected and classified by using the ISO 14155:2020 definition, as defined below. All DDs reported directly to the investigational center staff by a subject and those experienced by the investigational center staff will be reported on the appropriate eCRF. In addition, an eCRF should also be completed by the investigational center staff for each reported DD that did not lead to an Adverse Event. A DD that results in an AE should be captured on an AE CRF only.

Subjects participating in the study are expected to have mild irritation from device wear at times. Only discomfort occurring at a threshold resulting in early removal of the device should be reported as a DD or adverse event.

Device Deficiency (ISO 14155:2020)

A device deficiency is any inadequacy of a medical device with respect to its identity, quality, durability, reliability, usability, safety, or performance.

D00674412

Note 1 to entry: Device deficiencies include malfunctions, use errors, and inadequacy in the information supplied by the manufacturer including labeling.

Note 2 to entry: This definition includes device deficiencies related to the investigational medical device or the comparator.

Each DD will be assessed for SADE potential defined as:

A DD that did not lead to an Adverse Event, but could have led to a SADE:

- a) if either suitable action had not been taken,
- b) if intervention had not been made, or
- c) if circumstances had been less fortunate

To return a study device as part of a DD, the subject is to contact the investigational center staff, and the investigational center staff should then follow the study procedures for returning products with DDs. For a list of study devices that needs to be return to the sponsor, please consult your study materials.

It is the responsibility of the investigator to follow their EC reporting requirements.

14 Statistical Design and Methods

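### Section 13 defines SADE potential more narrowly than the reporting duty in 11.4, so a deficiency that caused a minor adverse event may not be flagged for authority reporting

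*Protocol*

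**What the plan says.** Protocol Section 13 sets the assessment rule. It opens broadly, "Each DD will be assessed for SADE potential defined as", and then gives the definition: "A DD that did not lead to an Adverse Event, but could have led to a SADE", under any of three conditions a) to c) on what might have gone differently. The same section directs where such cases are recorded: "A DD that results in an AE should be captured on an AE CRF only".

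Protocol 11.4 sets the reporting rules at two levels.

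- **Site to sponsor.** The narrative reads "All severe hypoglycemia, DKA, SAE, SADE, and DD with SADE potential should be reported immediately to Medtronic (but not later than 72 hours". Table 8 gives a longer list for the same time limit, "Immediately, but no later than 72 hours after" site awareness. That list adds the adverse device effect (ADE) with no condition on seriousness. Its entry for deficiencies that might have led to a SADE refers the reader to Section 13.
- **Sponsor to authority.** Item b) of the events reportable in the EU is "any device deficiency that might have led to a serious adverse event if appropriate action had not been taken". Table 9 gives 7 calendar days for deficiencies that may have led to a SADE, and 2 calendar days where there is imminent risk needing prompt remedial action. Its UK rows carry the same two limits.

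Table 10 in 11.5 has both the investigator and the sponsor classify deficiencies with SADE potential.

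**The concern.** SADE potential is the label that site and sponsor are told to apply, and Section 13 is the only place that defines it. Item b) and Table 9 ask only whether the deficiency could have led to something serious. Section 13 adds a second test, that no AE of any kind occurred. A deficiency that did some harm and could have done serious harm fails the second test, while the same deficiency with no harm passes it. The rule therefore becomes less sensitive as the outcome moves closer to harm.

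At stake is whether such cases are recognised as reportable to the authority. The participants are aged 2 to 6. The CE-marked pump, sensor and transmitter are used outside their approved indication, and arm A2 uses an investigational pump and sensor.

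**Working it through.** No arithmetic applies: there is no stated figure to reproduce and no event count to compute. The check follows a deficiency through the definitions and reporting tables.

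**Step 1: is an AE caused by a deficiency always an ADE?** The deficiency definition in Section 13 includes malfunctions, use errors and inadequate manufacturer information. The ADE definition in 11.2 includes AEs arising from malfunction, use error and inadequate instructions. Section 11.2 also says that device in its definitions means any device used in the study. So an AE that results from a deficiency is an ADE.

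**Step 2: follow three outcomes of a deficiency that could have led to a SADE.**

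| Actual outcome | SADE potential by Section 13 | Site to sponsor, Table 8 | Authority report, wording of 11.4 list and Table 9 |
|---|---|---|---|
| No AE | Yes | 72 hours, as a deficiency | Yes, 2 or 7 days |
| Non-serious AE | No, by definition | 72 hours, as an ADE | Yes, 2 or 7 days |
| Serious AE | No, by definition, but it is a SADE | 72 hours, as a SADE | Yes, as a device-related serious event |

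Only in the middle row does the Section 13 label disagree with the authority duty with no other trigger to make up for it. In the third row the event qualifies through its own seriousness.

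**Step 3: an example from the protocol's own list.** Section 11.3 gives an insertion-site infection as an ADE, and cellulitis at the site requiring hospitalization as a serious one. Assume that a device defect caused the infection and that it was treated without hospitalization. The defect led to a non-serious AE and, in less fortunate circumstances, could have led to the SADE. Item b) and Table 9 cover it. Section 13 gives it no SADE potential.

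**Step 4: does another rule flag the case?** The Clinical Events Committee's required list in 12.1 names serious events, SADEs, unanticipated SADEs, severe hypoglycemia and diabetic ketoacidosis (DKA). It does not name non-serious ADEs in general or deficiencies with SADE potential. The Data Monitoring Committee (12.2) reviews the rate of device-related AEs periodically; its listed tasks do not include classifying single cases. Sponsor review under 11.5 does reach every event, but it classifies by the term that Section 13 defines.

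**Step 5: consistency within 11.4.** The narrative's immediate list omits the ADE, while Table 8 includes it. The 72-hour notice in the middle row therefore rests on Table 8 alone.

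**The case against.** The strongest answer is that other text already catches the case. Three further readings are tempting, and the documents do not support them.

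1. *A reader might infer that the case escapes expedited reporting.* It does not. Table 8 puts every ADE, serious or not, on the same 72-hour clock as serious events.
2. *A reader might infer that the case meets no trigger in Table 9.* Table 9 and item b) neither use the SADE-potential label nor cite Section 13, and neither requires that no AE occurred. Read alone, they cover the case. What remains is the risk that it is not recognised.
3. *A reader might infer that the near-misses closest to serious harm drop out, such as ketosis caught early after an infusion failure.* Section 11.3 treats glycemic excursions short of severe hypoglycemia or DKA as expected and not reportable as AEs. On that reading no AE occurred and Section 13 applies normally. If intervention was needed to prevent life-threatening illness, the serious-event definition may apply. The affected class is mainly non-glycemic device events, plus any severe hypoglycemia caused by a deficiency and rated non-serious.

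It can also be said that the sponsor reviews all AEs and deficiencies (11.5), that recording a case on the AE form does not in itself exempt it from assessment, and that the form, held under separate cover, may already carry a suitable item.

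All of this stands and limits the consequence. It does not remove the mismatch: a sponsor reviewer who applies Section 13 as written must answer no for every deficiency linked to an AE.

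**Conclusion.** The definition in Section 13 is narrower than the duty it feeds and should be corrected. As written, it excludes every deficiency that led to a non-serious AE, whatever that deficiency might have caused. The consequence is limited: the sponsor still learns of the event within 72 hours and the authority duty still applies, but the classification step meant to identify such cases does not, so a 2- or 7-day report could be missed.

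The size in cases is unknown, since the documents give no expected number. The rule covers all study devices and all phases. SAP 7.10.3 counts deficiencies without using SADE potential, and SAP 7.5.2 plans no tests on safety endpoints, so no planned estimate or test depends on this definition.

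The conclusion assumes that site and sponsor apply Section 13 literally and that the AE form, which was not available, has no separate SADE-potential item.

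**What to change.** 1. In Section 13, define SADE potential as any deficiency, whether or not it led to a non-serious AE, that could have led to a SADE under conditions a) to c). This matches item b) and Table 9.
2. State in Section 13 that recording a deficiency on the AE form only does not exempt it from this assessment. If the AE form has no SADE-potential item, add one.
3. Reconcile the 11.4 narrative with Table 8 on whether ADEs belong in the immediate-report list.

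The cost is one changed sentence and one clarification in Section 13, an edit to 11.4, possibly one form item, and a few more assessments and expedited reports.
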